6.2. Preparation, Handling, Storage, and Accountability

1. The investigator or designee must confirm appropriate conditions (eg, temperature) have been maintained during transit for all study interventions received and any discrepancies are reported and resolved before use of the study intervention.
2. Only participants enrolled in the study may receive study intervention and only authorized site staff may supply, prepare, and/or administer study intervention.
3. All study interventions must be stored in a secure, environmentally controlled, and monitored (manual or automated recording) area in accordance with the labeled storage conditions with access limited to the investigator and authorized site staff. At a minimum, daily minimum and maximum temperatures for all site storage locations must be documented and available upon request. Data for nonworking days must indicate the minimum and maximum temperatures since previously documented for upon return to business.
4. Any excursions from the study intervention label storage conditions should be reported to Pfizer upon discovery along with any actions taken. The site should actively pursue options for returning the study intervention to the labeled storage conditions, as soon as possible. Once an excursion is identified, the study intervention must be quarantined and not used until Pfizer provides permission to use the study intervention. Specific details regarding the excursion definition and information to report for each excursion will be provided to the site in the CRU site procedures.
5. Any storage conditions stated in the SRSD will be superseded by the storage conditions stated on the label.
6. Study interventions should be stored in their original containers.

7. The investigator, institution, or the head of the medical institution (where applicable) or authorized site staff is responsible for study intervention accountability, reconciliation, and record maintenance (ie, receipt, reconciliation, and final disposition records), such as the IPAL or sponsor-approved equivalent. All study interventions will be accounted for using a study intervention accountability form/record.
8. Further guidance and information for the final disposition of unused study interventions are provided in the CRU's site procedures. All destruction must be adequately documented. If destruction is authorized to take place at the investigator site, the investigator must ensure that the materials are destroyed in compliance with applicable environmental regulations, institutional policy, and any special instructions provided by Pfizer.

Upon identification of a product complaint, notify the sponsor within 1 business day of discovery.

6.2.1. Preparation and Dispensing

Within this protocol, preparation refers to the investigator site activities performed to make the study intervention ready for administration or dispensing to the participant by qualified staff. Dispensing is defined as the provision of study intervention, concomitant treatments, and accompanying information by qualified staff member(s) to a healthcare provider, participant in accordance with this protocol. Local health authority regulations or investigator site guidelines may use alternative terms for these activities.

Nirmatrelvir **CCI** tablets will be dispensed at the CRU into individual dosing containers by 2 operators, 1 of whom is an appropriately qualified and experienced member of the study staff (eg, physician, nurse, physician's assistant, nurse practitioner, pharmacy assistant/technician, or pharmacist). The tablets will be labeled in accordance with Pfizer regulations and the clinical site's labeling requirements.

Commercial ritonavir (Norvir® or other local commercialized product) oral tablets will be dispensed at the CRU into individual dosing containers using the package insert as guidance by 2 operators, 1 of whom is an appropriately qualified and experienced member of the study staff (eg, physician, nurse, physician's assistant, nurse practitioner, pharmacy assistant/technician, or pharmacist). The tablets will be labeled in accordance with Pfizer regulations and the clinical site's labeling requirements.

Nirmatrelvir/ritonavir oral powder will be prepared at the CRU in the individual dosing containers by 2 operators, 1 of whom is an appropriately qualified and experienced member of the study staff (eg, physician, nurse, physician's assistant, nurse practitioner, pharmacy assistant/technician, or pharmacist). Details of dose preparations, volume/amount of food vehicle, will be given in the EDR. Prepared doses will be labeled in accordance with Pfizer regulations and the investigator site's labeling requirements.

6.3. Assignment to Study Intervention

The investigator's knowledge of the treatment should not influence the decision to enroll a particular participant or affect the order in which participants are enrolled.

The investigator will assign participant numbers to the participants as they are screened for the study. Pfizer will provide a randomization schedule to the investigator and, in accordance with the randomization numbers, the participant will receive the study treatment regimen assigned to the corresponding randomization number.

6.4. Blinding

This is an open-label study.

6.5. Study Intervention Compliance

As participants are dosed at the site, they will receive study intervention directly from the investigator or designee, under medical supervision. The date and time of each dose administered in the CRU will be recorded in the source documents and recorded in the CRF. The dose of study intervention and study participant identification will be confirmed at the time of dosing by a member of the study site staff. Study site personnel will examine each participant's mouth to ensure that the study intervention was ingested.

6.6. Dose Modification

No dose modification is anticipated.

6.7. Continued Access to Study Intervention After the End of the Study

No study intervention will be provided to participants at the end of their study participation.

6.8. Treatment of Overdose

For this study, any dose of nirmatrelvir greater than CCI or ritonavir CCI within a 24-hour time period [± 2 hours] will be considered an overdose.

There is no specific treatment for an overdose.

In the event of an overdose, the investigator should:

1. Contact the medical monitor within 24 hours.
2. Closely monitor the participant for any AEs/SAEs and laboratory abnormalities as medically appropriate and at least until the next scheduled follow-up.
3. Document the quantity of the excess dose as well as the duration of the overdose in the CRF.
4. Overdose is reportable to Pfizer Safety **only when associated with an SAE**.

5. Obtain a blood sample for PK analysis within 1 day from the date of the last dose of study intervention if requested by the medical monitor (determined on a case-by-case basis).

Decisions regarding dose interruptions or modifications will be made by the investigator in consultation with the medical monitor as needed based on the clinical evaluation of the participant.

6.9. Prior and Concomitant Therapy

Participants will abstain from all concomitant treatments, except for the treatment of adverse events and hormonal contraceptives that meet the requirements of this study in participants who are WOCBP (see [Appendix 4](#)).

Use of prescription or nonprescription drugs and dietary and herbal supplements are prohibited within 7 days or 5 half-lives (whichever is longer) prior to the first dose of study intervention. Limited use of nonprescription medications that are not believed to affect participant safety or the overall results of the study may be permitted on a case-by-case basis following approval by the sponsor. Acetaminophen/paracetamol may be used at doses of ≤ 1 g/day.

As nirmatrelvir and ritonavir are both primarily metabolized by CYP3A4, concomitant use of any medications or substances that are strong inducers of CYP3A4 are prohibited within 28 days prior to dosing of study intervention. Additionally, ritonavir and nirmatrelvir are inhibitors of CYP3A4. Therefore, medications highly dependent on CYP3A4 for clearance and for which elevated plasma concentrations may be associated with serious and/or life-threatening events are not permitted during dosing of nirmatrelvir/ritonavir, through 4 days after the last dose of nirmatrelvir/ritonavir.

All concomitant treatments taken during the study must be recorded with indication, daily dose, and start and stop dates of administration. All participants will be questioned about concomitant treatment at each site visit.

Treatments taken within 28 days before the first dose of study intervention will be documented as a prior treatment. Treatments taken after the first dose of study intervention will be documented as concomitant treatments.

6.9.1. Rescue Medicine

There is no rescue therapy to reverse the AEs observed with nirmatrelvir or ritonavir; standard medical supportive care must be provided to manage the AEs.

7. DISCONTINUATION OF STUDY INTERVENTION AND PARTICIPANT DISCONTINUATION/WITHDRAWAL

7.1. Discontinuation of Study Intervention

It may be necessary for a participant to permanently discontinue study intervention. Reasons for permanent discontinuation of study intervention include the following.

- AE requiring discontinuation in investigator's view;
- Pregnancy;
- Positive COVID-19 test.

If study intervention is permanently discontinued, the participant will not remain in the study for further evaluation. See the [SoA](#) for data to be collected at the time of discontinuation of study intervention.

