7.2. Participant Discontinuation/Withdrawal From the Study

A participant may withdraw from the study at any time at his/her own request. Reasons for discontinuation from the study include the following:

- Refused further study procedures;
- Lost to follow-up;
- Death;
- Study terminated by sponsor;
- Investigator's decision;
- Pregnancy.

PFIZER CONFIDENTIAL

At the time of discontinuing from the study, if possible, an early discontinuation visit should be conducted. See the [SoA](#) for assessments to be collected at the time of study discontinuation and follow-up and for any further evaluations that need to be completed.

The early discontinuation visit applies only to participants who are enrolled/randomized and then are prematurely withdrawn from the study. Participants should be questioned regarding their reason for withdrawal.

The participant will be permanently discontinued from the study intervention and the study at that time.

If a participant withdraws from the study, he/she may request destruction of any remaining samples taken and not tested, and the investigator must document any such requests in the site study records and notify the sponsor accordingly.

If the participant withdraws from the study and also withdraws consent (see Section 7.2.1) for disclosure of future information, no further evaluations should be performed and no additional data should be collected. The sponsor may retain and continue to use any data collected before such withdrawal of consent.

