7.2.1. Withdrawal of Consent

Participants who request to discontinue receipt of study intervention will remain in the study and must continue to be followed for protocol-specified follow-up procedures. The only exception to this is when a participant specifically withdraws consent for any further contact with them or persons previously authorized by the participant to provide this information. Participants should notify the investigator in writing of the decision to withdraw consent from future follow-up, whenever possible. The withdrawal of consent should be explained in detail in the medical records by the investigator, as to whether the withdrawal is only from further receipt of study intervention or also from study procedures and/or posttreatment study follow-up, and entered on the appropriate CRF page. In the event that vital status (whether the participant is alive or dead) is being measured, publicly available information should be used to determine vital status only as appropriately directed in accordance with local law.

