8.4.1. Time Period and Frequency for Collecting AE and SAE Information

The time period for actively eliciting and collecting AEs and SAEs (“active collection period”) for each participant begins from the time the participant provides informed consent, which is obtained before undergoing any study-related procedure and/or receiving study intervention), through and including a minimum of 28 calendar days, except as indicated below, after the last administration of the study intervention.

Follow-up by the investigator continues throughout the active collection period and until the AE or SAE or its sequelae resolve or stabilize at a level acceptable to the investigator.

When a clinically important AE remains ongoing at the end of the active collection period, follow-up by the investigator continues until the AE or SAE or its sequelae resolve or stabilize at a level acceptable to the investigator and Pfizer concurs with that assessment.

For participants who are screen failures, the active collection period ends when screen failure status is determined.

If the participant withdraws from the study and also withdraws consent for the collection of future information, the active collection period ends when consent is withdrawn.

If a participant permanently discontinues or temporarily discontinues study intervention because of an AE or SAE, the AE or SAE must be recorded on the CRF and the SAE reported using the CT SAE Report Form.

Investigators are not obligated to actively seek information on AEs or SAEs after the participant has concluded study participation. However, if the investigator learns of any SAE, including a death, at any time after a participant has completed the study, and they consider the event to be reasonably related to the study intervention, the investigator must promptly report the SAE to Pfizer using the CT SAE Report Form.

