3.5.1. Adverse Events

Any adverse events occurring following start of treatment will be considered as treatment emergent adverse event (TEAE). Events that occur during follow-up within the lag time of up to 28 days after the last of nirmatrelvir/ritonavir dose will be counted as treatment emergent and attributed to the last treatment taken. Events that occur during the washout period (up to 28 days from the last treatment) between study periods will be counted as treatment emergent and attributed to the previous treatment taken. The time period for collecting AEs (“active collection period”) for each participant begins from the time the participant provides informed consent.

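### Protocol 7.1 ends evaluation when dosing stops for good, but 8.4.1, the follow-up contact and the SAP window assume 28 days of AE collection, so later new AEs could go uncollected

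*Protocol*

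**What the plan says.** Protocol 7.1 gives three reasons for permanent discontinuation of study intervention. The first is "AE requiring discontinuation in investigator's view"; the others are pregnancy and a positive COVID-19 test. It then says: "If study intervention is permanently discontinued, the participant will not remain in the study for further evaluation". The only collection it mentions is by reference to the SoA "for data to be collected at the time of discontinuation of study intervention".

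Protocol 7.2, on leaving the study, adds: "At the time of discontinuing from the study, if possible, an early discontinuation visit should be conducted". It refers to the SoA for assessments at that point and for follow-up.

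Protocol 7.2.1, under the heading of withdrawal of consent, says: "Participants who request to discontinue receipt of study intervention will remain in the study and must continue to be followed for protocol-specified follow-up procedures". It continues: "The only exception to this is when a participant specifically withdraws consent for any further contact with them", or with people authorized to speak for them.

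Protocol 8.4.1 runs active AE collection for each participant from consent "through and including a minimum of 28 calendar days, except as indicated below, after the last administration of the study intervention". The early ends it goes on to name are screen failure and withdrawn consent. Its closing paragraph removes the duty to look actively for AEs once a participant's time in the study is over.

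Protocol 4.1 and the SoA notes schedule a follow-up contact 28 to 35 days after the final dose. SAP 3.5.1 begins its follow-up rule with "Events that occur during follow-up within the lag time of up to 28 days after the last" dose; such events count as treatment emergent and are attributed to the last treatment taken. SAP 2.1 records no departure from the protocol's analysis plan, so the SAP does not settle the matter.

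**The concern.** TEAEs are a secondary endpoint, and the SAP defines them over a window reaching 28 days past the last dose. That definition works only if someone is asking about AEs throughout the window. Read on its own, 7.1 takes a participant out of the study when dosing stops for good, and one of the three reasons for stopping is an adverse event. The plan would then count events over a period in which, for these participants, the protocol may not have required anyone to look. A table showing no later events for such a participant could mean that none occurred or that none were sought, and the reader could not tell which.

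**Working it through.** The plan states no figure on this point, so the check is a comparison of the sections.

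| Section | Who it covers | After dosing stops |
|---|---|---|
| Protocol 7.1 | Anyone whose dosing is permanently discontinued | Leaves the study; SoA data at that time |
| Protocol 7.2 | Anyone leaving the study early | Early discontinuation visit if possible; SoA for follow-up |
| Protocol 7.2.1 | Those who request to stop dosing | Stays in the study and is followed, unless consent to contact is withdrawn |
| Protocol 8.4.1, collection period | Each participant | Active AE collection for at least 28 days after the last dose |
| Protocol 8.4.1, closing paragraph | Those whose participation is over | No duty to seek AEs actively |
| Protocol 4.1 and SoA note | Participants, not limited to completers | Contact 28 to 35 days after the final dose |
| SAP 3.5.1 | All TEAE reporting | Events to 28 days after the last dose count |

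**Step 1: is there a direct conflict?** Take a participant stopped by the investigator for an AE who has not withdrawn consent. Under 7.1 evaluation ends. Under 8.4.1 active collection runs at least 28 more days, because stopping dosing is not among the named early ends. Both cannot hold. Section 7.2.1 points the same way as 8.4.1, but literally covers only those who ask to stop, so the main conflict is with 8.4.1.

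**Step 2: does 8.4.1 resolve it?** Not fully. If 7.1 is taken to end participation, the closing paragraph of 8.4.1 removes the duty to seek AEs, and a site could cite the protocol for stopping. If the 28-day minimum governs, the sentence in 7.1 is wrong. The text does not say which has priority.

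**Step 3: do other sections show the same tension?** Yes. Section 7.1.2 discontinues a participant with confirmed creatinine findings from the study and then asks that participant to return for evaluation. Section 8.4.5.1 collects pregnancy details until 28 days after the last dose and follows the pregnancy to its end, although pregnancy is a 7.1 reason for stopping.

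**Step 4: which events are exposed?** Not the event that led to the stop: 8.4.1 requires it on the CRF, and 8.4.1 and 8.4.3 require follow-up until it resolves or stabilizes. The exposed events are new ones that begin after the early discontinuation visit.

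**Step 5: how long is the gap for one participant?** Assume 7.1 is followed literally and the last contact falls 0 to 4 days after the last dose. This range is my assumption, not a figure from the plan.

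- Last contact on the day of dosing: 28 − 0 = 28 days, 28/28 = 100% of the window.
- Last contact 4 days later: 28 − 4 = 24 days, 24/28 = 86% of the window.

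This measures time without active collection for that participant. It is not a count of events lost.

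**The case against.** The strongest reply is that a site reading the whole protocol already has its instructions. Section 8.4.1 sets the 28-day period for each participant, 4.1 and the SoA note call for the contact without limiting it to completers, and 7.2 sends early leavers to the SoA for follow-up. Further evaluation in 7.1 might mean only the remaining scheduled procedures. This stands as a limit on the harm: loss of data is possible, not certain. It does not remove the inconsistency, because 7.1 carries no such qualification and the closing paragraph of 8.4.1 supports the opposite reading.

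Three stronger readings are tempting, and the documents do not support them.

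- *TEAEs would be selectively under-counted by treatment.* No dose remains to be discontinued after Period 5, so the rule affects only participants who would otherwise have been dosed again. For them SAP 3.5.1 attributes washout events to the previous treatment, and a continuing participant's attribution normally passes to the next treatment at the next dose. With the minimum 4-day washout, the shortfall against continuing participants is about 4 days at most. The longer gap concerns each participant's own safety follow-up.
- *PK sampling would be cut short and AUClast biased.* No section says that sampling stops mid-period. SAP 5.3.1 sets underivable parameters to missing and excludes estimates known to be biased, and protocol 9.5 allows replacement.
- *One case means 8% of TEAEs lost.* One participant in 12 is 1/12 = 8.3% of the planned participants. It says nothing about the share of events.

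**Conclusion.** The concern holds as an inconsistency in the protocol with a limited safety-data consequence. Section 7.1 conflicts with the 28-day collection period in 8.4.1, the 28 to 35 day contact and the SAP window, and sits badly with 7.2.1. A site could, on a literal reading, stop eliciting new AEs after the early discontinuation visit, leaving 24 to 28 of the 28 days without active collection for that participant under the assumption in step 5. The documents give no expected discontinuation rate, so the number of such participants cannot be estimated and may be zero. The SoA column marks for early termination and follow-up could not be read reliably in the text available, so nothing here rests on them. The relative bioavailability analysis is not called into question.

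**What to change.** Reconcile 7.1, 7.2, 7.2.1, 8.4.1 and the SoA so that they give one statement of whether AE collection through 28 days after the last dose, and the 28 to 35 day contact, apply to participants whose dosing is stopped for good. That statement should cover both those stopped by the investigator and those who ask to stop, and should make clear when participation counts as concluded for the closing paragraph of 8.4.1. Whatever is decided should agree with the TEAE window in SAP 3.5.1. Which rule applies is for the clinical team; the statistical requirement is that the collection period and the counting window match.

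The cost is protocol wording, through whatever amendment step it requires. The follow-up contact is already in the SoA, so the reconciliation need not add a new visit or assessment.

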7.1.1. ECG Changes

A participant who meets either bulleted criterion based on the average of triplicate ECG readings will be withdrawn from the study intervention.

- QTcF >500 msec;
- Change from baseline: QTcF >60 msec.

If a clinically significant finding is identified (including, but not limited to, changes from baseline in QTcF after enrollment), the investigator or qualified designee will determine if the participant can continue in the study and if any change in participant management is needed. This review of the ECG printed at the time of collection must be documented. Any new clinically relevant finding should be reported as an AE.

